Getting Healthy is a 7-module website with interactive features aimed at reducing cardiovascular risk through healthier lifestyle choices. Modules are: Nutrition Center, Physical Activity, Healthier Kids, Weight Management, Stress Management, Quit Smoking, and Workplace Wellness. Each of the modules has a separate URL. Participants can sign up for a monthly e-newsletter. Getting Healthy does not have its own dedicated online community. We will e-mail a link to a new module weekly in order to parallel the seven weeks of PSFW+ sessions, and will send two email reminders and one text (if the subject agrees to receive text messages) weekly to prompt users to visit the module, as well as a reminder phone call after 10 days of non-use to parallel the adherence protocol in the PSFW+ condition. We estimate that each module will take an average reader 15-30 minutes to complete which corresponds closely to the time requirement for PSFW+ written content. Legacy will create a “portal page” that will require control participants to log in, generating data regarding website use. At the time of enrollment, the research assistant will introduce the participant to the portal page. Following entry of a unique username and password that will be assigned during enrollment, participants will be routed to the Getting Healthy module of the week. This approach will optimize attention matching and will also allow the team to collect basic Getting Healthy utilization metrics.]]

PSFW+: Positively Smoke Free on the Web plus Online Social Network PSFW+ participants will be registered on the website by the research assistants following randomization. Each participant's unique Study ID will be tied to his/her website registration to enable linkage of website utilization metrics with other data collected during the trial. Registration involves creating a username and password, entering an email address, and a mobile phone number (if available). The participant will receive a confirmation email following registration that contains a link to the site and instructions to bookmark it in his/her Internet browser for easy access.

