Outcome expectations	
 - Improvement in respiratory status - Monetary savings - Urges/cravings for cigs - Weight gain - Enhanced health/longevity 	
 - Possible worsening of depression/anxiety - Weight gain (desirable outcome for many PLWH) 	
 - Perceived Risks and Benefits Questionnaire
Short term			
 - CES-D
Long term		
 - Better long-term CD4+, VL, and survival 	
 - State-Trait Anxiety Scale

Tobacco Use (Aim 1 measures): Self-reported 7-day ppa will be measured at each follow-up and biochemically verified by exhaled carbon monoxide (ECO) at each study visit. Staff will be trained in the use, maintenance, and calibration of the Bedfont piCO+ Smokerlyzer. An ECO measurement of <10 ppm will be considered abstinent and of ≥10 ppm non-abstinent.²³ Discordant self-report and ECO data because of marijuana effects on ECO will be clarified with saliva cotinine strips.¹²⁹ Secondary outcomes include standardized items from the CDC Question Inventory on Tobacco (CDC-QIT)⁹¹ including number of quit attempts, continuous abstinence, and 30-day ppa. Daily cigarette and other tobacco consumption and age at initiation will be assessed. Nicotine addiction will be measured with the Fagerström Tolerance Questionnaire,¹³⁰ and the Contemplation Ladder will measure readiness to quit.¹³¹

Proposed Mediators (Aim 2 measures): Perceived social support will be measured with the Multidimensional Scale of Perceived Social Support to assess perceived general support arising from family, friends, and significant others.^{80,132,133} Smoking-specific social support will be measured with an adapted version of the Partner Interaction Questionnaire.¹⁹ The UCLA Loneliness Scale⁸³ will measure subjective feelings of loneliness or social isolation. [name] Social Support Scale for Smokers (OS4)¹³⁴ – will be adapted to assess dimensions of perceived support from the PSFW+ online community.

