Additional Control and Evaluation Measures: Other treatment exposure: Using standard assessment items administered in previous trials,¹⁴³ we will assess use of other cessation treatments including alternative smoking cessation websites, non-study NRT, prescription medications (e.g. varenicline), behavioral treatments (pamphlet/book, live and/or telephone counseling), and alternative quit methods (e.g., acupuncture, hypnosis). Individuals who report use of cessation websites will be asked to identify each specific website and the number of visits. [[Information about membership in any other health-promoting or tobacco treatment online communities will be collected from all subjects.]] **Treatment Satisfaction Questionnaire:** PSFW+ participants will be asked the number of times they visited the website, the approximate length of each visit, and ratings of overall satisfaction and perceived helpfulness of the site. Participants who report that they did not visit the website will be asked for specific reasons for non-use (e.g., lost Internet access, lack of interest, etc.). Similar questions will be asked regarding the Getting Healthy website. Additional questions will address knowledge of and familiarity with PSFW+ and Getting Healthy; these questions will be designed to detect potential study contamination. **PSFW+ Utilization Metrics:** We will extract the following utilization variables: date/time of registration, # site visits, date/time of each visit, # page views, date/time of each page view, # page views per session, # interactive component clicks, changes to personal profile (e.g., email, username), whether the user signed up for text messages, # text messages sent, and # emails sent to participant from the system. We will also extract the following variables from the Vanilla Forums database specific to community utilization: # clicks through to the community from PSFW+ content pages, # direct visits to the community, # discussion posts, # comments, # private messages sent/received, # wall posts made/received, and whether or not they customized their profile (e.g., photo). Getting Healthy utilization metrics will rely on data collected from the portal page (3.C.4.e.) and subjects' historical recall. At the end of Visit 2, we will administer the 18-item Sense of Virtual Community scale to PSFW+ participants.

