Missing data. We expect less than 10% missing data at any time. Under an intention-to-treat approach, participants who had been considered non-smokers up to the point of losing contact will be considered relapsers at future data points. Multiple imputation methods¹⁴⁶ will be used to deal with missing data, assuming a missing at random (MAR) mechanism; we will generate 10 multiple imputed datasets, analyze each dataset separately, and then combine the results across the 10 datasets using Rubin's method.

3.C.6.c. Specific Aim 2: Mediator Analyses. Aim 2 hypothesizes that greater social support mediates the intervention-cessation relationship. Figure 3 depicts our mediational model:

X represents treatment group, **Z** represents the hypothesized mediator (e.g., perceived social support), **Y** represents outcome (7-day ppa), **a** is the regression path between treatment group and mediator, **b** is the regression path between mediator and outcome, and **c'** is the regression path between treatment group and outcome controlling for the effect of the mediator. The 3-month assessment will be used for mediator **Z** and the 6-month measure of 7-day ppa will be used as the primary binary outcome **Y**. To increase statistical power of our mediation analysis we will use the product of coefficients method.¹⁴⁷ We will estimate the coefficient **a** by fitting a linear regression model with the putative mediator as the continuous outcome, treatment arm as the main predictor, and covariates identified in bivariate analyses as being associated with social support. We will estimate the coefficient **b** by using a logistic regression model with abstinence as the binary outcome, **Z** as the main predictor, and covariates identified in bivariate analyses as being associated with abstinence. We will then calculate the mediated effect as the corresponding product of these coefficients with standard error and 95% confidence interval estimated according to MacKinnon.¹⁴⁸ Since the sampling distribution of this product shows considerable skewness and kurtosis, interval estimation will be based upon bias-corrected and accelerated (BCA) bootstrap confidence intervals.¹⁴⁹ Potential mediators in Figure 1 will be analyzed separately, and additional analyses will be conducted to evaluate interaction effects.

Figure 3. Mediational Analyses

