Subject Attrition. Loss to follow-up will be minimized through the use of standard tracking/contact sheets, reminder calls/emails/texts, incentives linked to follow-up completion (\$30 cash each visit), and provision of travel fare for all study visits. We will emphasize that incentives are not dependent on website usage or on abstinence, but rather on completion of study visits. Retention rates have been high in our previous clinical trials: during 7 years of participation in Community Programs for Clinical Research on AIDS (CPCRA) trials, MMC ranked in the top 3 sites nationally for retention, losing <2% of subjects from long-term follow-up. Retention rate within various clinical trials (e.g., ACTG, WIHS, HPTN) at MGUH are also impressively high (98%). The aggregate loss to follow-up rate in the three tobacco treatment RCTs conducted in the MMC ID Clinic has been 4.8%.

Study Condition Contamination. To prevent contamination (i.e., subjects accessing non-assigned study websites), we will record control participants' email address at the time of study enrollment in a database linked to the PSFW+ data store. Control participants who attempt to register on PSFW+ using a recorded email address will be redirected to the welcome page of the Getting Healthy site. It is also conceivable that control subjects will register on PSFW+ with a different email address. We will probe for this occurrence and for PLWH+ utilization of the Getting Healthy website in the Treatment Satisfaction Questionnaire at follow-up and will adjust the analyses accordingly.

Generalizability. Once efficacy is established in this controlled trial with optimal recruitment and in-person assessment protocols, future dissemination studies will be conducted that will prioritize external validity.

3.C.8. Timeline and Benchmarks for Success: **Months 0-9:** Modifications and enhancements to PSFW+ including adherence prompts, technical strategies to minimize contamination, efforts to grow and evaluate online community, refinement of assessment protocols, programming of ACASI systems. **Months 10-54:** Recruitment and follow-up at 1, 3- and 6-months, with the final follow-up in Month 54. Preliminary data analyses will be conducted throughout the project.

Months 55-60:

Final outcome analyses and manuscript preparation.

Benchmarks for success:

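### The OS4 is listed as an Aim 2 mediator but asks only about the PSFW+ community, so the planned two-arm mediation analysis and its power statement do not work for that scale

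*Combined protocol and SAP*

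**What the plan says.** The Proposed Mediators paragraph of 3.C.5 names four instruments for Aim 2: the Multidimensional Scale of Perceived Social Support, an adapted Partner Interaction Questionnaire, the UCLA Loneliness Scale, and the OS4. The OS4 "will be adapted to assess dimensions of perceived support from the PSFW+ online community".

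On the control arm, 3.C.4.e states that "Getting Healthy does not have its own dedicated online community". Section 3.C.7 adds a barrier: "Control participants who attempt to register on PSFW+ using a recorded email address will be redirected" to the Getting Healthy welcome page.

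Section 3.C.6.c uses the product of coefficients. Path a is estimated "by fitting a linear regression model with the putative mediator as the continuous outcome, treatment arm as the main predictor". Path b comes from a "logistic regression model with abstinence as the binary outcome"; that sentence names the mediator and covariates as predictors, but not treatment arm. The mediator is taken at 3 months, and each mediator is analysed on its own.

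Section 3.C.6.e claims power of 80% or more for each mediator at a=0.14, b=0.14 and N=508. No section gives a control version of the OS4, a scoring rule for controls, or an exception to the two-arm method.

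**The concern.** A product-of-coefficients analysis needs the mediator in both arms, because path a is the between-arm difference in that mediator. A scale that refers only to a community supplied to one arm has nothing comparable in the other. The plan nevertheless puts the OS4 through the same model as the other three scales and covers it with the same power claim.

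At stake is one listed mediator in a secondary aim. Its indirect effect would either be impossible to report, or be reported as a number driven by who was assigned to PSFW+. It is the only Aim 2 scale specific to online support, so readers would look to it for evidence on the mechanism.

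**Working it through.** **Inputs.** From 3.C.6.e: abstinence 15.4% vs 7.5%, 254 per arm, power 0.8, alpha 0.05, a=b=0.14, N=508. From 3.C.4.d: 1:1 allocation. Sidedness is not stated; two-sided is assumed because it reproduces the plan's figure.

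**1. The plan's own figures.** Two-proportion formula, pooled variance under the null, no continuity correction, mean rate 0.1145:

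n = [1.96·√(2·0.1145·0.8855) + 0.8416·√(0.154·0.846 + 0.075·0.925)]² / (0.154 − 0.075)² = (0.8826 + 0.3761)² / 0.006241 ≈ 254 per arm.

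Two arms give 508, so the Aim 2 figure counts both arms.

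Mediation power at a=b=0.14 and N=508, with treatment scaled to SD 1, unit residual variances and a continuous outcome:
- Joint significance: each path has power Φ(0.14·√508 − 1.96) = Φ(1.195) = 0.884, and 0.884² = 0.78.
- Simulated bias-corrected bootstrap (no acceleration term): 0.82 to 0.84.
- Simulated percentile bootstrap: 0.75 to 0.77.

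The claim of 80% or more is therefore reproduced by the bias-corrected bootstrap, for a mediator observed in all 508 participants.

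**2. Path a for the OS4 if only PSFW+ participants have scores.** Without covariates, a = mean(OS4 | PSFW+) − mean(OS4 | control). The second term has no observations. In regression terms, the intercept column and the treatment column are both all ones, so the design matrix has rank 1 instead of 2. Neither a nor a·b is identified. A larger sample does not change this, and neither does the bootstrap or the binary outcome.

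**3. What can still be estimated.** Only the association between OS4 score and abstinence within PSFW+. At n=254 and b=0.14, with the same approximation: Φ(0.14·√254 − 1.96) = Φ(0.271) = 0.61, against 0.88 for path b at N=508.

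**4. Path a if controls answer at the floor.** The plan does not specify this case; it is examined as the other possible outcome. Set every control score to 0 and let PSFW+ scores have mean m and SD 1, with m assumed to be 1 to 3. Then a = m − 0 = m, the PSFW+ mean itself. With equal arms, the correlation between arm and mediator is m/√(2 + m²): 0.58 for m=1, 0.82 for m=2, 0.90 for m=3.

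Path b was then simulated with 254 per arm, abstinence of 15.4% and 7.5%, and no effect of support within the arm (400 runs per row):

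| m | path b significant, arm omitted | path b significant, arm included |
|---|---|---|
| 1 | 38% | 4% |
| 2 | 61% | 5% |
| 3 | 69% | 4% |

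With arm omitted, as the path b sentence reads, the treatment effect on abstinence is passed to the mediator. With arm included, the false-positive rate returns to about 5%, but path a still reflects assignment only.

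**The case against.** The strongest reply is that the plan nowhere says controls skip the OS4. Section 3.C.5 describes self-report measures by ACASI without splitting by arm. Where one arm is meant, the text says so: the Sense of Virtual Community scale is given to PSFW+ participants. Section 3.C.7 also allows that a control might register on PSFW+ under another email address. This stands: the absence of control values is a strong inference from the scale's referent and the design, not stated text. It does not rescue the analysis, because controls asked about a community they were not given would mostly answer at the floor.

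A second reply is that 3.C.6.c points to mediators in Figure 1, which is not shown, so whether the OS4 appears there cannot be checked. That is fair, but 3.C.5 names it as an Aim 2 measure. Its absence from Table 2 shows little, since the Multidimensional Scale is not there either.

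Stronger readings are tempting but unsupported:
- *Aim 2 fails.* It does not. Three scales can be measured in both arms. H2 concerns changes in perceived support, and 3.C.5 assigns perceived social support to the Multidimensional Scale. A scale about a community joined after randomisation has no meaningful baseline for change.
- *The plan scores controls zero, making the OS4 a near copy of treatment.* No such rule is stated, and a correlation of 0.58 to 0.90 under assumed means is not always a near copy.
- *The test reduces to whether the score predicts abstinence within PSFW+.* That holds only if arm is in the path b model, and the path b sentence does not name it.
- *The most relevant mediator is lost.* The documents do not rank the four scales.

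**Conclusion.** The point holds for one of the four Aim 2 scales. As planned, path a for the OS4 is either not identified or an artefact of assignment, so the stated power for each mediator at N=508 cannot cover it. The within-PSFW+ association remains estimable, at roughly 61% power for b=0.14.

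This rests on three assumptions: controls either do not answer the OS4 or answer at its floor; about 254 PSFW+ participants are available; and the continuous-outcome approximation serves as a guide for a binary outcome. The identification result does not depend on the last two. Aim 1 is unaffected, and H2 can be tested with the other three scales.

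**What to change.** Preferred: state that the OS4 is not part of the two-arm Aim 2 mediation analysis. Analyse it as a process measure within PSFW+, alongside the Sense of Virtual Community scale, and limit the power statement in 3.C.6.e to mediators measured in both arms. State also whether controls were given the scale. This costs a few sentences and needs no new data, which matters because the 2021 amendment records that the parent study closed in 2020.

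Alternative, only where questionnaires can still be changed: word the scale as support from any online community or website, give it to both arms, and include treatment arm in the path b model. The plan already has a related item for everyone ("Information about membership in any other health-promoting or tobacco treatment online communities will be collected from all subjects"), although it asks about membership and not perceived support. The cost is a few extra control-arm items, low and skewed control scores, and a somewhat broader construct than support from the PSFW+ community.

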Potential Moderators and Mediators (Exploratory Aim): Potential **moderators** include demographic variables (age, gender, race, ethnicity), clinical variables (e.g. HIV risk behavior, most recent CD4+ and viral load, histories of cardiovascular, pulmonary, neoplastic disease, and substance use assessed with the NIH/NIAID Baseline Substance Use Self-Report),¹³⁵ depression (Center for Epidemiologic Studies Depression Scale),¹³⁶ and anxiety (State-Trait Anxiety Scale).¹³⁷ Potential **mediators** include: 1) tobacco knowledge measured using standardized items from the Adult Use of Tobacco Survey;⁹¹ 2) self-efficacy measured with the Self-Efficacy/Temptation Scale;¹³⁸ 3) Smoking Decisional Balance (Short Form);¹³⁹ 4) risks and benefits of smoking measured with the Perceived Risks/Benefits Questionnaire;¹⁴⁰ modified to include HIV-referent questions (e.g. "Does smoking raise/lower your CD4+ count?"); 5) PSFW+ and attention-placebo utilization metrics as described in the next section; and 6) use of NRT and other quit methods. NRT use will be assessed with the 4-item Morisky Scale;¹⁴¹ side effects,¹⁴² dosage, duration of use, pattern of use ("on and off" vs. "everyday"), and continued smoking while using NRT will be assessed.

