Specimens, Records, or Data: Enrolled subjects will complete measures (**see Table 2**) in a private office using an ACASI interface on a password-protected study computer. Study staff will be nearby to render any assistance necessary. Input data will be maintained on the computer's hard drive and will be uploaded on the day of questionnaire completion via a secure Sharepoint portal to the AECOM Epidemiology Informatics/Study Management Unit (EISMU - please see Protection of Study Data below and the AECOM Resources section). Exhaled carbon monoxide measurements will be performed according to manufacturer's instructions and discordant abstinence data (frequently observed in marijuana users) will be clarified with saliva cotinine strips. Biochemical validation results will be keyed by study staff into the study databases. All locally maintained computer data will be stored on password protected computers/servers and backed up to encrypted Ironkey USB drives.

Website utilization metrics will be extracted from the back end of the PSFW+ intervention. These metrics include 1) an event tracking database within the PSFW+ application for non-community related actions, and 2) community related data from the Vanilla Forums database. From the event tracking database within the PSFW+ application we will extract individual-level metrics utilization including the date/time of each session and page visited, date/time of each site login, the referring URL for each site visit, the date/time of registration, number of clicks through to the community (date/time stamped), number of page views per session (date/time stamped), number of interactive component clicked (date/time stamped), and changes to profile such as email or username. We will also track the number of email and text messages sent to each participant as a function of the individually tailored adherence strategies we will employ for this study. From the Vanilla Forums database, we will extract individual-level tracking metrics including (among others) visits, number of discussions participated in, number of comments made, number of private messages sent/received, number of profile posts made/received, and whether a custom profile photo was uploaded.

For subjects in the control condition, time and duration of each login to Getting Healthy via the portal page will be recorded. Email and text message reminder data will be compiled in the same manner as the PSFW+ condition.

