Materials Access: During the course of the project, the Investigators, Data Analyst, Software Development Team, Community Administrator, and Project Manager will have access to individually identifiable information about human subjects. In addition, Vanilla Forums technical and support staff will have access to registration data and any data arising from participation in the online community. This access is detailed in the Vanilla Forums Terms of Service and Privacy Policy which are referenced in the PSFW+ documents. The Getting Healthy website will have access to users' IP addresses, but these users will not be distinguishable from any other user of the AHA Getting Healthy site. These various levels of access will also be listed in the participant informed consent document.

Protection of Study Data: All data in transit will be transmitted with security precautions. Data moving between application server and database or other data stores will be secured via Secure Socket Layer (SSL). Data from the PSFW+ application database will be transferred to Legacy's local servers via direct SSL connection with the database and stored on secure servers with restricted access rights. Data from the Vanilla Forums community software will be transferred to Legacy's local servers via SFTP ("Secure File Transfer Protocol" or "FTP over SSL"). Personally identifiable data (e.g. phone number, email address) associated with the PSFW+ application will be encrypted in the database.

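### Dose is planned as a between-arm mediator, but use is logged in-site for PSFW+ and only by portal login plus recall for controls, so an arm difference in dose could come from measurement

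*Combined protocol and SAP*

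**What the plan says.** **Role of dose.** The Exploratory Aim (section 2) names dose of intervention as a potential mediator. Section 3.C.5, under potential moderators and mediators, gives as item 5 "PSFW+ and attention-placebo utilization metrics as described in the next section". Section 3.C.6.d says exploratory mediation follows 3.C.6.c, where path a is a linear regression of the mediator on treatment arm and path b a logistic regression of abstinence on the mediator. Section 3.C.6.b also plans secondary analyses of treatment intensity.

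**PSFW+ capture (3.C.5).** "We will extract the following utilization variables: date/time of registration, # site visits, date/time of each visit, # page views", and the list goes on to page views per session and interactive clicks. For the online community: "We will also extract the following variables from the Vanilla Forums database specific to community utilization".

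**Control capture.** Under 3.C.4.e controls log in at a portal page, after which "participants will be routed to the Getting Healthy module of the week". Section 3.C.5 says that "Getting Healthy utilization metrics will rely on data collected from the portal page (3.C.4.e" and, in the same sentence, on participants' recall. Section 5.A (Sources of Materials) adds that "time and duration of each login to Getting Healthy via the portal page will be recorded". Section 5.A (Materials Access) says of the external site that "these users will not be distinguishable from any other user of the AHA Getting Healthy site".

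**Self-report.** The Treatment Satisfaction Questionnaire in 3.C.5 asks PSFW+ participants for the number and approximate length of visits, and puts similar questions to controls.

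**The concern.** Path a is meant to show that assignment changed the amount of programme use. If one arm's use is recorded in more detail, or more completely, path a also contains the difference in recording. That difference then enters the product of coefficients. If path b is non-zero, the trial could conclude that PSFW+ worked through greater engagement when engagement was equal.

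The plan leaves the choice of dose metric open. It defines no common dose variable and does not confine metrics that exist in only one arm to within-arm analysis. Any between-arm dose analysis under 3.C.6.b would have the same weakness.

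**Working it through.** **1. What each arm records**

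| Measure | PSFW+ | Control |
|---|---|---|
| Visits or logins, with time | Site log | Portal login |
| Page views, interactive clicks | Site log | None planned |
| Community activity | Forum database | No dedicated community |
| Duration | Timed visits and page views | Duration of portal login (5.A); the plan does not say how this is observed after the redirect |
| Self-reported number and length of visits | Asked | Similar questions asked |

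Rows 2 and 3 cannot be compared between arms. Rows 1 and 5 can, with a caveat on row 1. Each control module has its own URL and a module link is e-mailed weekly (3.C.4.e), but the plan does not say whether that link passes through the portal. A visit made directly to a module would not be logged.

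**2. The plan's own sample size.** The documents give no figure for the dose mediator, so I take the per-arm number from Aim 1 (3.C.6.e: 15.4% vs 7.5%, power 0.8, alpha 0.05). With p̄ = 0.1145:

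n = [1.960·√(2·0.1145·0.8855) + 0.842·√(0.154·0.846 + 0.075·0.925)]² / 0.079² = 254 per arm.

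This matches the stated figure (two-sided, pooled variance, no continuity correction).

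**3. Path a with equal true use.** Inputs: mean use 5.5 sessions (the pilot mean, 3.C.1.e); 254 per arm; SD assumed 2 to 3, because none is given; control capture q assumed, because no bypass share is given.

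- False gap = 5.5·(1 − q)
- SE = SD·√(2/254)
- P(path a significant) ≈ Φ(gap/SE − 1.96)

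Example, q = 0.90 and SD 2.5: gap 0.55; SE = 2.5·0.0887 = 0.222; z = 2.48; probability about 70%.

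| Control capture | False gap (sessions) | SD 2 | SD 2.5 | SD 3 |
|---|---|---|---|---|
| 100% | 0 | 5% | 5% | 5% |
| 95% | 0.275 | 34% | 24% | 18% |
| 90% | 0.55 | 87% | 70% | 54% |
| 80% | 1.10 | 100% | 99.9% | 98.5% |

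A gap of (1.960 + 0.842)·√(2/254) = 0.25 SD is enough for 80% power on path a.

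**4. From a false path a to false mediation.** Simulation, 1,500 runs per row, 254 per arm:

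- True use has the same distribution in both arms (mean 5.5, SD 2.5).
- Each control session is recorded with probability q.
- Abstinence at mean use is 15.4% vs 7.5%.
- Mediation is flagged when paths a and b are both significant with the same sign. This stands in for the plan's bootstrap interval.

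| Effect of true use on quitting | Arm in path b model | 100% captured | 90% | 80% | 50% |
|---|---|---|---|---|---|
| None | Yes | 0.1% | 2.0% | 2.5% | 2.7% |
| None | No | 0.2% | 3.9% | 9.2% | 33% |
| Log OR 0.2 per session (assumed) | Yes | 1.7% | 67% | 93% | 90% |
| Log OR 0.2 per session (assumed) | No | 3.1% | 69% | 98% | 99% |

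The row for arm omitted matters because 3.C.6.c lists only the mediator and covariates in the path b model, although it describes c′ as the treatment path controlling for the mediator. The text can be read either way.

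**The case against.** The best reply is that the plan already collects comparable data. Login or visit counts exist in both arms, and so does self-report. A reader might infer that controls are measured by the portal alone and that nothing is on one scale; the documents do not support that.

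Bypass is also unproven. The portal requires a login and staff introduce it at enrolment. The statement that users cannot be distinguished on the external site is a confidentiality statement about what that site sees, and does not describe portal capture. How the portal is built is not described, so whether it can observe time on the external site is unknown. These replies stand, and they make every capture figure above an assumption.

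A reader might also infer that the analysis would necessarily find mediation. It would not. If dose has no effect on quitting and arm is in the path b model, under-capture produces a false flag in only about 2% to 3% of trials. The programme's own sign of a dose effect (18% abstinent among completers of all 8 sessions, against 10.1% overall, 3.C.1.e) comes from PSFW users only. It does not show that visiting a cardiovascular site predicts quitting.

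Nor is there a planned check of attention matching that these counts would spoil. The 8 sessions against 7 modules are a minor matter, since both programmes run over seven weeks.

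Finally, the analysis is exploratory, and dose is one of six listed mediators. That limits the consequence. It does not supply the missing definition of dose or a rule keeping one-arm metrics out of a between-arm model.

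**Conclusion.** The point holds in a limited form. The asymmetry in capture and the use of both arms' metrics as a mediator are in the text. For page views, clicks and community metrics, an arm effect would follow from measurement or design. For visit counts it could arise from modest under-capture: at 10% loss in controls, path a is falsely significant in about 54% to 87% of trials (SD 2 to 3, mean 5.5, 254 per arm, equal true use).

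False mediation needs a further condition: either use predicts quitting (67% at 90% capture under the assumed log OR of 0.2, SD 2.5), or arm is omitted from path b (3.9% at 90% capture and 33% at 50%, even with no dose effect). The SD, the capture share and the log OR are assumptions.

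The primary intent-to-treat comparison and the Aim 2 social-support mediation are untouched. The plan should be corrected here, but the trial's main conclusion does not depend on it.

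**What to change.** In 3.C.5 and 3.C.6.d, and for any between-arm dose analysis under 3.C.6.b:

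- Define one between-arm dose measure in the same way for both arms, for example the number of programme weeks (1 to 7) with at least one login.
- Give self-reported number of visits, worded identically in both arms, as the companion or sensitivity measure. Weekly logins still miss a week in which every control visit bypassed the portal, and recall has errors of its own, so agreement between the two is informative. Which of them leads is a matter of judgement.
- State that treatment arm is included in the path b model.
- Use page views, clicks, session counts and community metrics only for dose-response within PSFW+.
- Send every control e-mail and text link through the portal login, if that is still possible. The amendment dated 10-4-21 says the parent study closed in 2020, so this may now be only a limitation to report.
- Do not treat control duration (5.A) as time on site unless the portal can observe it.

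Cost: analysis-plan wording and, if still open, a link setting. No new data are needed, provided the self-report items were worded alike. The drawback is that the common measure is cruder than the PSFW+ server logs.
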